**Table 3. Schedule of Activities and Measurements.**

Activities/Measurements	PS	Screening Visits			RI	RZ	Each Feeding Period (FP1, FP2, FP3, & FP4)				
		SV1	SV2	SV3			W1	W2	W3	W4	W5
Informed consent	o	o+w				w					
Randomization to diet order						✓					
Feeding activities incl. diary					daily		daily-----				
Clinical Assessments & Physical Measurements											
Blood pressure (seated)		✓	✓	✓			✓ 	✓	✓	✓ 	
Weight		✓		✓	✓ 	✓ 	✓ 	✓ 	✓ 	✓ 	✓ 
Height		✓									
Orthostatic blood pressure				✓						✓	
Dietitian evaluation			✓								
Biospecimen Collection & Laboratory Assessments											
HbA1c point-of-care testing		✓									
Non-fasting blood draw			✓ 					✓ 			
Fasting blood draw 				✓						✓	
Spot urine collection 				✓						✓ 	
24-hour urine collection 			✓							✓	
Stool sample			✓							✓	
Self-monitoring blood glucose					✓ 		✓ 	✓ 	✓ 	✓ 	✓ 
Questionnaires/Forms											
Prescreening	✓										
Demographic		✓									
Medical history		✓									
Medications		✓		✓		✓	✓	✓	✓	✓	✓
Dietary information		✓									
Contact information		✓									
Dietary recall			✓	✓							
Symptoms				✓							✓
Diet acceptability											✓
CGM Ancillary Study (optional) 											
Continuous glucose monitoring			✓  -----							✓  -----	
Symptom reporting survey			✓  -----							✓  -----	

o=oral consent, w=written consent

W1 BP is to be measured on day 1 of each feeding period (FP)

W4-W5 BP measured on 5 days during the last 2 weeks of each FP, including ≥2 in W5

Weight measured on each day of on-site feeding during RI and re-measured prior to RZ if not measured within the past 7 days

Weight measured 3 times per week (typically on each day of on-site feeding or food pick-up)

CMP assayed, including serum potassium and creatinine to calculate eGFR for eligibility

Only for participants at-risk for hyperkalemia (see section 10.3): serum potassium assayed for safety monitoring; should occur ~W2 D1

CMP with lipids assayed, and stored specimens (serum, plasma, whole blood, PAXgene)

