#### **Feeding Period Weeks 1-3 (FP#W1-3)**

BP will be measured on day 1 of the first week (FP#W1D1) and then weekly during weeks 2 (FP#W2) and 3 (FP#W3).

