#### **Feeding Period Weeks 4-5 (FP#W4-5; “End-of-period” measures)**

During the last two weeks of each feeding period, BP will be measured on 5 days, at least 2 of which will be during the last week of the intervention period. In addition, participants will be asked to collect a 24-hr urine and a stool sample at home and return the specimens to the clinic. A fasting blood specimen will be drawn and a spot urine will be collected. Participants will also complete (1) a symptom questionnaire, (2) a diet acceptability questionnaire, and (3) an orthostatic hypotension assessment.

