### *Low Blood Pressure Reading*

The diets being tested have been shown to lower BP in the general population. When combined with anti-hypertensive medications, the dietary interventions being studied in DASH4D might further lower blood pressure, which is often asymptomatic and which, long-term, has been shown to reduce the risk of cardiovascular and kidney disease. Still, some persons might experience symptoms, such as lightheadedness, and other problems (abnormal laboratory tests). Assessment of low BP readings is complicated because BP readings are exceedingly variable, such that frequent monitoring will detect low readings without clinical consequence.

In this context, we will identify randomized participants with low readings, defined by a systolic blood pressure < 90 mmHg. If the average of the triplicate set of systolic BP readings on a given day is < 90 mmHg, the BP form will flag completion of the Hypotension Event form. Staff will ask the participant if he/she is currently feeling lightheaded or dizzy. If yes, staff will contact a study clinician for guidance while the participant is at the clinic; if no, a study clinician will receive an automatic alert from REDCap and will contact the participant within 2 days to assess symptoms of low BP and any possible explanations for the low reading. Repeat BP readings will be obtained within 8 days (or sooner, if appropriate). If the BP remains < 90 mmHg or the participant is determined to be at risk of low blood pressure, the participant will be advised to see their health care provider responsible for treating their BP for evaluation and possible adjustment of anti-hypertensive medications, or, with permission, the study clinician will directly contact the participant's health care provider.

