  - g. Diet acceptability, as rated by participants on two questions with a 9-point Likert scale for how much the participant liked the diet (1=disliked extremely, 9=liked extremely) and how hungry the participant felt while eating the diet (1=not at all hungry, 9=extremely hungry)

Additionally, safety outcomes including hypoglycemia, hypokalemia, hyperkalemia, elevated BP, low BP, serious adverse events [SAEs], and adverse medical events, which are assessed throughout each of the intervention periods, will also be documented for and compared across the study diets.

- 1.2.8 To conduct subgroup analyses (by gender, race, age, baseline level of the outcome variable [i.e., BP for the primary and secondary outcomes], baseline number of medications used to treat the outcome, and chronic kidney disease [CKD] status), corresponding to the above aims.
- 1.2.9 To establish a repository of biospecimens (plasma, serum, urine, stool, PAXgene).

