Secondary 1.2.6	DBP	Same as all of above for SBP	
Secondary 1.2.7	fasting glucose; glycated albumin; fructosamine; HbA1c; plasma lipids; 24-hour urinary albumin excretion; CVD risk score; patient-reported outcomes	End of Period	CH vs DL; DH vs DL; CH vs CL; DH vs CH; DL vs CL; (DH-DL) vs (CH-CL)*
	safety data (incl. hypoglycemia, hyperkalemia, elevated BP, low BP, SAEs & adverse medical events)	Cumulative over the entire period	CH vs DL; DH vs DL; CH vs CL; DH vs CH; DL vs CL; (DH-DL) vs (CH-CL)*
Secondary 1.2.8	All of above, by pre-specified subgroups		

\*examination of interaction (difference of differences)

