#### 4.6 Evaluations for other outcomes

The contrasts of other outcomes include evaluating the mean difference of end-of-period fasting glucose, fructosamine, and plasma lipid levels; estimated CVD risk derived from the ACC/AHA ASCVD risk

equation; postural changes in systolic and diastolic BP; and diet acceptability patient rating scales between DL and CH diets, between lower and higher sodium level within the DASH4D and comparison diets, and between the DASH4D and comparison diet at each sodium level.

The analyses for the plasma lipid measures will be carried out similarly to analysis for the primary outcome of SBP using an observed data likelihood approach implemented through mixed-effects regression models (e.g., Model 1), anchored on the MAR assumption (see **4.2.1**, **4.3** and **4.4**). Appropriate transformation of the outcome will be carried out when necessary to satisfy relevant model assumptions. Similarly, sensitivity analysis under NMAR scenarios using multiple imputation will be carried out to examine the robustness of the finding under MAR (see **4.2.4**), as well as sensitivity analysis to address relevant medication changes (see **4.2.3**).

The safety outcomes are counts of binary outcomes collected throughout the feeding period, and SAEs and adverse medical events are similar count data (Poisson outcomes) that will be collected throughout the feeding period per trial protocol. We will evaluate the differences of the safety outcomes between DL and CH diets, between lower and higher sodium levels within the DASH4D and comparison diets, and between the DASH4D and comparison diets at each sodium level. The total number of events and the number of persons experiencing 1 or more events will be reported.

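### Elevated-BP and low-BP safety events are counted from day 1 of each feeding period, a reading that reflects the preceding own-food break, and this pulls ratio-scale diet contrasts modestly toward no difference

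*Combined protocol and SAP*

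**What the plan says.** **Counting window.** The table of aims in SAP 4.1 lists elevated BP and low BP among the safety data for Aim 1.2.7. It gives their timing as "Cumulative over the entire period" and lists six diet contrasts. SAP 1.2.7 describes safety outcomes "which are assessed throughout each of the intervention periods, will also be documented for and compared across the study diets". SAP 4.6 agrees: "The safety outcomes are counts of binary outcomes collected throughout the feeding period". Counts are modelled by GEE with a log link and binary outcomes with a logit link. No section excludes day 1 or sets a lag.

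**BP schedule.** For weeks 1-3, protocol 8.1 says "BP will be measured on day 1 of the first week (FP#W1D1) and then weekly during weeks 2 (FP#W2) and 3 (FP#W3". For weeks 4-5 it says "During the last two weeks of each feeding period, BP will be measured on 5 days". Table 3 confirms that the week-1 BP is taken on day 1 of every feeding period. According to SAP 4.1, periods 2 to 4 each follow at least 1 week (typically 2) of own food. Period 1 follows a 6-8 day run-in on sample menus from all four diets (protocol 8.1).

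**What triggers an event.** For low BP, protocol 10.3 acts on any single day: "If the average of the triplicate set of systolic BP readings on a given day is < 90 mmHg". For elevated BP it has two escape levels. The higher (systolic above 180 or diastolic above 110 mmHg) acts on one reading. The lower (171-180 or 106-110 mmHg) leads to referral only if a repeat within 7 days is also in or above that range. Neither rule treats day 1 differently. The SAP does not say which of these makes an analysed event.

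**The concern.** A day-1 BP describes the state in which a participant arrives, not the effect of a diet begun that day. Under the whole-period window, an event triggered by that reading is still charged to the new diet. Diet order is randomized and balanced across sequences (protocol 7.3), so the chance of a day-1 event should be about the same whichever diet is starting. A common background added to both sides of a ratio moves it toward 1, so the direction of the error is known in advance.

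The primary and secondary outcomes avoid this because they use only the last 2 weeks of each period. The BP safety outcomes have no such protection. At stake is how faithfully the relative frequency of high and low readings on each diet is reported. Low BP was added as a risk in protocol v2.3.

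**Working it through.** **1. Weight of the day-1 reading.** Scheduled BP days per period: 1 (day 1) + 1 (week 2) + 1 (week 3) + 5 (weeks 4-5) = 8. This reproduces the maximum of 8 SBP measurements in SAP 4.4. Day 1 is 1/8 = 12.5% of scheduled BP days.

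**2. Effect on a count ratio.** Let pA and pB be the per-reading event rates on two diets and p0 the day-1 rate, the same for both.

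- Ratio without day 1: pA / pB.
- Ratio with day 1: (7·pA + p0) / (7·pB + p0).
- Difference in expected counts with day 1: (7·pA + p0) − (7·pB + p0) = 7·(pA − pB), so p0 cancels.

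For an on-diet ratio of 2.0 (pB = 1, pA = 2):

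| Day-1 rate p0 | Calculation | Ratio |
|---|---|---|
| lower diet rate | (14 + 1)/(7 + 1) | 1.88 |
| midway | (14 + 1.5)/(7 + 1.5) | 1.82 |
| higher diet rate | (14 + 2)/(7 + 2) | 1.78 |
| twice the higher rate | (14 + 4)/(7 + 4) | 1.64 |

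With p0 near 0 there is no dilution. Over the same p0 range, a ratio of 1.5 becomes 1.44 to 1.35 and a ratio of 3.0 becomes 2.75 to 2.08.

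**3. Illustration on the BP scale.** DL is the DASH4D diet with lower sodium and CH the comparison diet with higher sodium. Assumptions not in the documents:

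- Daily SBP is normal and the CH mean is 135 mmHg.
- The day-1 mean lies between the DL-CH midpoint and 135.
- Every single day above 170 (cut at 170.5) or below 90 counts as an event.

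From the SAP 3 power table come the SD of 14, a DL effect of 4.7 mmHg (the MDD at N = 100, SD 14, r = 0.5) and the DASH-Sodium effect of 8.9 mmHg.

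Worked case, elevated BP at 4.7 mmHg: p(CH) = 0.00561, p(DL) = 0.00204, p0 = 0.00343 at the midpoint. Without day 1 the ratio is 0.00204/0.00561 = 0.36. With day 1 it is (7·0.00204 + 0.00343)/(7·0.00561 + 0.00343) = 0.0177/0.0427 = 0.42.

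| DL/CH ratio | Without day 1 | Day-1 mean at midpoint | Day-1 mean at 135 |
|---|---|---|---|
| SBP >170, 4.7 mmHg | 0.36 | 0.42 | 0.44 |
| SBP >170, 8.9 mmHg | 0.14 | 0.18 | 0.24 |
| SBP <90, 4.7 mmHg | 3.05 | 2.64 | 2.80 |
| SBP <90, 8.9 mmHg | 7.6 | 5.7 | 6.8 |

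On the log scale, elevated and low BP shift about equally when the day-1 mean is at the midpoint. As the day-1 mean rises, elevated BP is diluted more and low BP less. At 4 mmHg above CH, the low-BP ratio moves only from 3.05 to 2.96, or from 7.6 to 7.3.

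**4. Number of events behind the ratios.** Same inputs, 100 participants, 7 later days (700·p):

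- Above 170: CH 3.9; DL 1.4 (4.7 mmHg) or 0.5 (8.9 mmHg).
- Below 90: CH 0.5; DL 1.4 or 3.5.
- Day 1 adds 0.2-0.6 elevated and 0.07-0.19 low readings per diet.
- Above 180 only: CH about 0.4.

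The approximate Poisson SE of a log ratio is √(1/E1 + 1/E2), for example √(1/3.9 + 1/1.4) ≈ 1.0 for elevated BP and √(1/0.46 + 1/1.40) ≈ 1.7 for low BP at 4.7 mmHg. The largest shift in the table, ln(0.24/0.14) ≈ 0.5-0.6, is well below its SE of about 1.5.

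**5. Second model.** A simulation used between-person SD 12, day-to-day SD 9, CH mean 135 and an own-food mean from 4 below to 4 above CH. The direction was the same. At a 4 mmHg effect, the elevated-BP CH:DL count ratio fell from about 2.1 to between 1.98 and 1.70. The low-BP DL:CH ratio fell from about 2.3 to between 2.0 and 2.26. At 8.9 mmHg the figures were about 5.7 to 4.4-2.8, and about 5.9 to 4.7-5.7.

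**The case against.** Counting from the first feeding day is a recognised exposure-window convention. It loses no safety information, and SAP 4.6 also reports total events and persons affected. The contrasts are non-primary, and SAP 4.1.4 calls for caution in reading them. With so few events, the shift is smaller than the sampling error. All of this stands and limits how much weight the point can carry. It does not remove a bias whose direction is known and whose repair is simple.

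A reader might infer several stronger things that the documents do not support:

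- *That the plan hides a low-BP harm.* Under the step 3 inputs, day 1 supplies only about 2-8% of the low readings charged to DL. Protocol 10.3 suggests that even the comparison diet with higher sodium may improve on many participants' usual diet. Own-food BP would then be high and the low-BP dilution smaller still.
- *That a large share of elevated readings on DL is spurious.* The same model puts day 1 at 19-51% of them, but 51% is about 0.56 of 1.1 readings. It also counts every lone reading of 171-180, which protocol 10.3 refers only after a confirming repeat.
- *That day-1 events are charged to the wrong study diet.* SAP 4.2.2 does not expect carryover. Its 6-week spacing argument concerns end-of-period outcomes and does not cover a day-1 reading about a week after the last diet, but nothing in the documents shows that an effect persists that long.
- *That the reading strictly precedes exposure.* The documents do not say whether the day-1 BP comes before the first study meal. At most, hours of exposure are possible.

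**Conclusion.** The point holds in a limited form. The whole-period window includes one scheduled BP day in eight that reflects own food or run-in rather than the assigned diet, and nothing in the SAP sets it apart. On the log and logit scales this pulls the elevated-BP and low-BP contrasts modestly toward no difference. The pull is greater for elevated BP than for low BP provided that own-food BP sits nearer to CH than to DL, or above CH. Expected absolute count differences and the primary and secondary BP outcomes are not affected.

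The conclusion rests on the day-1 event rate being about equal across diets, which follows from randomized, balanced order and no material carryover. The numerical shifts also depend on assumed means and SDs and on an event definition that the SAP does not give. They show direction and rough scale and do not predict the trial's results. The change is worth making because it is specific and nearly free, not because it is likely to alter a conclusion.

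**What to change.** Change the analysis text only, in SAP 4.1 and 4.6:

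1. State what counts as an analysed elevated-BP event and a low-BP event, including whether a reading in the lower escape range counts without its repeat.
2. For the diet contrasts, take both outcomes from readings after day 1 of the feeding period.
3. Do not count a repeat prompted solely by a day-1 reading as a new on-diet event. Otherwise the own-food signal returns through selected participants. Scheduled readings from week 2 onward count on their own terms.
4. List day-1 events separately as start-of-period findings, not attributed to a diet.
5. Report the whole-period count as a sensitivity analysis.

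Monitoring of day-1 readings and the response to them stay as they are. The cost is a few sentences, a date filter and a flag for repeats that trace back to day 1. The downside is slightly fewer counted events in contrasts that are already sparse.

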#### 4.1.1 Analytic population

All randomized participants who completed at least 1 day of intervention feeding and at least 1 end-of-period BP assessment will be included in the analyses, unless otherwise noted below. For practical reasons related to food preparation, there is an interval between date of randomization and initial day of feeding, and participants who were randomized but withdrew from the trial prior to any intervention feeding will not be included in analyses. Additionally, participants who did not complete at least 1 end-of-period BP assessment during the first feeding period (i.e., dropped out or withdrew within the first 3 weeks of the study) will be excluded from the analytic population, as the modelling approach depends on having at least 1 end-of-period BP data point.

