### ***Menu Cycle***

Each of four feeding periods lasts 5 weeks, during which time participants are provided all of their food, snacks, and most caloric beverages (see section on beverages below). The anticipated break between feeding periods will last 1 or more weeks; the break allows ad libitum food intake. We attempt to have participants complete their sequence of four diets during consecutive intervention feeding periods, but in some cases, participants may have a “gap” (due to the COVID epidemic, personal illness, personal circumstances, etc.) where they miss a feeding period. In situations with a missed intervention period, participants resume their randomized sequence of diets upon returning to finish out their four diets as assigned. Below is an example illustrating feeding with a one-period gap:

	Study Intervention Period 1	Study Intervention Period 2	Study Intervention Period 3	Study Intervention Period 4	Study Intervention Period 5
As planned	Assigned Diet #1 (Participant's FP1)	Assigned Diet #2 (Participant's FP2)	Assigned Diet #3 (Participant's FP3)	Assigned Diet #4 (Participant's FP4)	
With gap	Assigned Diet #1 (Participant's FP1)	Missed due to illness	Assigned Diet #2 (Participant's FP2)	Assigned Diet #3 (Participant's FP3)	Assigned Diet #4 (Participant's FP4)

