### *Hyperkalemia Monitoring and Management Protocol*

For at-risk participants, potassium levels will be checked at the end of week 1 of each intervention period. It is well-recognized that serum potassium may be falsely elevated due to issues with hemolysis of the lab specimen, so if the laboratory reports hemolysis, potassium will be rechecked within 3 days.

Hyperkalemia is defined as a serum potassium  $\geq 5.5$  mEq/L. If hyperkalemia is detected in the absence of hemolysis, investigators will follow the protocol outline in **Figure 3**. Mild hyperkalemia (potassium 5.5-5.9 mEq/L) will be rechecked within 3 days. Moderate hyperkalemia (potassium 6.0-6.4 mEq/L) will be rechecked in 1-2 days, and while awaiting results the participant's potassium-elevating medications will be held and their dietary potassium reduced to a low potassium diet ( $\leq 2400$  mg of potassium per day in total). Participants with moderate hyperkalemia whose potassium is normal on repeat testing will be tested again after reintroducing their study diet and held medications. Any participant with hyperkalemia on repeat testing, or a single potassium value  $\geq 6.5$  mEq/L, will be withdrawn from the study. Any participant withdrawn from the study for hyperkalemia will receive medical evaluation for hyperkalemia by a study clinician which may include referral to the emergency department, or making dietary or medication changes in coordination with the patient's healthcare provider.

Additionally, all participants will have potassium levels checked as part of their fasting laboratory panel at the end of each feeding period. If hyperkalemia occurs at this time in a participant at-risk for hyperkalemia, we will follow the hyperkalemia protocol as described below. If hyperkalemia occurs in a participant not at-risk, the laboratory will be rechecked and subsequent action will be at the discretion of the study clinician.

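### The BP-based analytic population in SAP 4.1.1 has no safety exception, so participants withdrawn early in the first feeding period leave the between-diet safety comparison

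*Combined protocol and SAP*

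**What the plan says.** SAP 4.1.1 opens by admitting randomized participants who "completed at least 1 day of intervention feeding and at least 1 end-of-period BP assessment". These participants "will be included in the analyses, unless otherwise noted below". Two sentences later it excludes "participants who did not complete at least 1 end-of-period BP assessment during the first feeding period", explained as "i.e., dropped out or withdrew within the first 3 weeks of the study". The justification is that the modelling needs one end-of-period BP value.

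Under protocol 8.1, end-of-period BP is measured on five days in weeks 4 and 5. BP readings in weeks 1 to 3 do not count as end-of-period.

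The aims table in SAP 4.1 counts safety outcomes over the entire feeding period. SAP 4.6 sets out the diet contrasts for safety and the GEE models, and promises that "The total number of events and the number of persons experiencing 1 or more events will be reported". It names no population of its own.

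Protocol 10.3 states: "For at-risk participants, potassium levels will be checked at the end of week 1 of each intervention period". It then withdraws participants whose hyperkalemia persists on repeat testing or who have one sufficiently high value. It also provides for withdrawal at very low potassium, and leaves withdrawal open after a BP escape level is met.

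**The concern.** The inclusion rule was written for a BP model but reaches every main-trial analysis that does not set its own rule, and safety is one of these. The protocol's own safety procedures can end participation before week 4 of the first period. Such a person has no end-of-period BP and so falls outside the population in which safety is compared.

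The events lost this way are those serious enough to stop participation. Whether an event counts also depends on when it happens. A week 1 withdrawal in the second period is counted if first-period BP was obtained; the same event on the same diet in the first period is not. If one diet causes more early withdrawals, dropping them makes that diet look closer to the others. Few such events are expected, so even one omission could change how the safety table reads.

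A smaller matter sits in the same section. Its opening sentence asks for one end-of-period BP and names no period, while its exclusion sentence asks for one in the first period.

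**Working it through.** **Safety: tracing one participant.**

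1. Randomized, starts the first feeding period and eats at least one day of study food: meets the feeding condition in SAP 4.1.1.
2. Potassium checked at the end of week 1, repeat test positive, withdrawn under protocol 10.3.
3. No week 4 or 5 BP in any period: fails the opening sentence of 4.1.1 and also its exclusion sentence. The result is the same on either reading.
4. SAP 4.6 notes no exception, so the person and the event are outside the safety comparison.
5. The multiple imputation for binary and count outcomes in SAP 4.1.2 fills missing values for people in the population. It does not bring back people outside it.

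**Safety: possible size.** The documents give no rate, so a range is assumed. Let q be a constant per-period risk of a withdrawal-causing event. The share of such events in period 1 is q / [1 − (1 − q)^4].

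- q = 0.005: 0.005 / 0.0199 = 25%, or 0.5 of 100 participants
- q = 0.05: 0.05 / 0.1855 = 27%, or 5 of 100 participants

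These are upper limits on the loss, because only events before the first end-of-period BP of period 1 are removed.

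**BP: the plan's own figures.** SAP 3 gives SD 14 mmHg, within-person correlation 0.75, N = 100, two-sided 0.05 and 90% power.

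- SD of the difference = 14 × √[2(1 − 0.75)] = 9.90, matching the stated 9.9.
- The minimal detectable difference is 3.21 mmHg by the normal formula and 3.24 by the paired t, against 3.34 stated. At 3.34 the t-based power is 91.6%. With N = 95 the t formula gives 3.33, so the table may allow for about 5% loss, though the SAP does not say so. This gap does not affect the present point.

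**BP: is first-period data needed?** Model 1 was set up with compound-symmetric covariance from these inputs and 96 participants spread over all 24 diet orders. That set of orders is an assumption, since the documents say only that order is balanced. With period 1 deleted for everyone, all 6 remaining parameters are estimable (rank 6 of 6), and the SE of the DL − CH contrast is 1.23. The model therefore does not require first-period data.

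**BP: cost of the first-period wording.** With N = 100 and complete data the SE of DL − CH is 0.990 (9.90/√100). Suppose some participants lack period 1 BP but have periods 2 to 4 (assumed numbers):

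| Affected of 100 | SE if kept | SE if dropped | Increase |
|---|---|---|---|
| 2 | 0.993 | 1.000 | 0.7% |
| 5 | 0.999 | 1.016 | 1.7% |
| 10 | 1.007 | 1.044 | 3.7% |

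**The case against.** The best defense is intent. The stated reason concerns BP only, and SAP 1.2.7 and 4.6 describe safety collection throughout the period without any BP condition, so the authors may well have meant to count everyone fed. That is plausible. But 4.1.1 states its own reach, and nothing later lifts it for safety. It is also true that adverse events go to the DSMB and IRB under protocol 10.4. That protects participants during the trial; it does not change who enters the reported comparison. The objection that few people are affected stands.

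Three stronger readings are tempting, and the documents do not support them.

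- A reader might project an event count from the feeding study described in protocol 10.3, with two confirmed hyperkalemia cases among 29 adults. The same sentence says both were taking medications, or combinations of them, that are exclusions here. The number of at-risk participants in this trial is not given either. The figure cannot serve as an expected rate.
- A reader might infer that usable BP data from periods 2 to 4 will be discarded, because protocol 7.1 says "In situations with a missed intervention period, participants resume their randomized sequence of diets upon returning to finish out their four diets as assigned". The example there shows a missed calendar slot after the first diet was completed, and the next diet is still that participant's own second period, so first-period BP is kept. The explanatory gloss in 4.1.1 and the rationale in the SAP change history both point to people with no end-of-period BP at all. The only exposed case is someone who stops before any week 4 or 5 BP in the first period and later returns. The documents do not describe that case. It would be rare, since one of five BP days is enough and assessments may run briefly into a sixth week.
- A reader might take the rule to govern every analysis. The per-protocol analyses (SAP 4.2.5) and the CGM ancillary study (Appendix B, 11.1) have their own rules.

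**Conclusion.** The safety point holds on the text and on either reading of 4.1.1: a participant withdrawn for good before the first end-of-period BP of the first period leaves the between-diet safety comparison. Withdrawals after that stay in. The number affected is not stated and is probably small. The 25% to 27% share rests on an assumed constant risk across periods and bounds the loss from above. The gap should still be closed, because the rule as written can omit protocol-driven safety withdrawals for a reason that has nothing to do with event counts.

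The BP point is an internal contradiction to reconcile. Even on the literal wording, its cost to the SE of the primary contrast is under 1% for 2 of 100 affected and about 4% for 10 of 100, assuming those people have complete data in periods 2 to 4.

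**What to change.** 1. Add one sentence to SAP 4.1.1, with a cross-reference in 4.6: safety outcomes are analyzed in everyone randomized who ate study food on at least one day of a feeding period, each event is attributed to the diet being eaten when it occurred, and no BP assessment is required.
2. In 4.1.1, delete the reference to the first feeding period from the exclusion sentence and align its gloss, so that the BP population needs one end-of-period BP in any feeding period. The opening sentence and the stated reason already imply this.

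The cost is two short edits and safety tables run on the wider set. No new data are needed, and the primary model does not change.
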